This proposed study is a prospective 12-week tobacco cessation trial using established methods and outcomes typical of tobacco cessation trials, but specifically recruiting co-users of cannabis to; 1) evaluate the impact of co-use on tobacco cessation (compared to tobacco only users), and 2) assess changes in cannabis use during tobacco treatment. Adult tobacco users (ages 18-40; N=208) who are motivated to quit smoking will be recruited. Cannabis co-users will be oversampled (2:1). All participants will receive a first-line tobacco cessation pharmacotherapy (varenicline) paired with a behavioral intervention to bolster abstinence (contingency management and psychosocial counseling) for 12 weeks, while cannabis use will not be specifically addressed. Biochemical verification and self-reports (through mobile daily diaries) of substance use will be collected throughout treatment. A subset of cannabis-tobacco co-use participants (N = 48) will engage in an additional ecological momentary assessment (EMA) portion of the study (EMA supplement) for granular observation of patterns of co-use.

Specific Aims of the proposed research are:

Aim #1: examine the impact of cannabis co-use on tobacco cessation among co-users compared to tobacco only users.

Hypothesis 1: Co-users will have lower rates of 7-day point prevalence abstinence from tobacco at the end of treatment (Week 12) compared to tobacco only users.

Aim #2: Among co-users, assess changes in cannabis use during tobacco cessation treatment.

Hypothesis 2: Co-users with moderate to high severity of nicotine dependence will demonstrate increases in concurrent cannabis use, while lower severity of nicotine dependence will yield no changes in cannabis use.

Exploratory Aim: To assess for a dose-dependent impact of cannabis use severity on tobacco cessation outcomes among co-users.

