A.1.b. Harms associated with co-use. Cannabis and tobacco co-use is associated with public health burden in the form of greater prevalence of psychiatric and psychosocial problems (27, 28), additive health risk (29), and lower self-reported ratings of health (30). There are also treatment-related concerns specific to co-use. Though prevalence of co-use is high, there is surprisingly little consensus regarding treatment recommendations and cessation strategies tailored for co-users. Few published studies of co-use treatment interventions exist and all have been pilot/feasibility trials (31-34). While co-use treatment is needed, the degree to which co-use affects treatment success for a single, targeted substance remains in question. Specifically, the impact of cannabis use on tobacco cessation outcomes is not well understood in the literature and may serve as an obstacle to successful tobacco cessation among co-users. Also unknown is the degree to which compensatory substance use (i.e., increased use) occurs as a result of reduction or cessation from the other substance. Though the harms resulting from continued tobacco use have been

demonstrated and several efficacious treatment strategies exist (35-39), there remain important barriers to successful tobacco cessation that must be addressed to improve abstinence outcomes for sub-populations of smokers.

A2. The Impact of Co-Use on Cessation Outcomes. Cannabis use has been associated with an increased risk of nicotine dependence and greater nicotine dependence among co-users (12, 40-43). However, the literature on tobacco cessation success among co-users has been mixed, fraught with methodological limitations, and to date, no prospective studies to inform tobacco treatment among co-users have been conducted. Some evidence, including recent studies, suggests that co-use has an adverse impact on tobacco outcomes. Specifically, cannabis co-use has been associated with lower rates of tobacco cessation when compared to non-cannabis users (44-50), lower levels of sustained tobacco abstinence, increased odds of relapse (51, 52), and lower odds of tobacco quit attempts (53).

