3.0 Study Endpoints

Below is a table of the study endpoints and outcomes.

Type	Name	Time Frame	Brief Description
Primary	7-day point prevalence tobacco abstinence at the end of treatment (Week 12)	Final 7 days of treatment (Week 12)	7-day point prevalence abstinence from tobacco at the end of treatment (Week 12) will be assessed via biochemical verification and participant self-report and rates of abstinence will be compared between cannabis co-users and tobacco only controls.
Secondary	Changes in cannabis use during tobacco cessation treatment (among co-users)	Final 4 weeks of study treatment (Weeks 8-12)	Among cannabis co-users, cannabis use rates and amounts during the final 4 weeks of tobacco treatment (Weeks 8-12) will be assessed and

			nicotine dependence will be the primary model predictor.
Other: Exploratory	Cannabis co-use severity on tobacco cessation (among co-users)	Throughout trial participation	Tobacco abstinence and indicators of tobacco reduction (average cigarettes per day, quantitative cotinine, etc.) throughout the trial will be examined as a function of baseline cannabis use severity (determined by days of use in the past 30) to assess for dose-dependent impact on tobacco outcomes based on cannabis use severity.

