10.0 Statistical Analysis and Data Management

Analytic Strategy.

Power and sample size. The proposed study is powered to detect a meaningful difference in end of treatment tobacco abstinence between cannabis co-users and tobacco only users. Secondarily, the study will assess the relationship between cannabis use patterns during treatment and nicotine dependence severity in co-users. Specific Aim #1: Examine the impact of cannabis co-use on tobacco cessation outcomes among co-users compared to tobacco only users. Hypothesis 1: Co-users will have lower rates of 7-day point prevalence abstinence from tobacco at the end of treatment (Week 12) compared to tobacco only users. In a cross-sectional survey of national household data (51), tobacco cessation was reported among 65.5% of respondents who endorsed no cannabis use as compared to 21.8% of tobacco cessation in those reporting current cannabis use ($\Delta=43\%$). Studies examining the efficacy of varenicline for tobacco cessation (108, 109) noted near 50%-point prevalence abstinence at treatment conclusion (Week 12) in the varenicline-treated group. Finally, in our recently completed adolescent varenicline trial (U01 DA0317779), youth cannabis co-users reported point prevalence tobacco abstinence in 20% of participants at Week 12 and 43% in those who use tobacco only (analysis with all available data). The proposed R01 study intends to apply a successful tobacco treatment (varenicline) paired with contingency management in treatment-seeking smokers. Assuming a similar abstinence rate in tobacco only users (45%) and a successful abstinence rate in participants who are cannabis co-users as compared to the adolescent study (20%; $\Delta=25\%$), to achieve 80% power with a 5% type 1 error rate, a sample of 82 participants in the cannabis co-using cohort and 41 in the tobacco only cohort. However, to account for the inclusion of 2 study sites in the design, an additional fixed factor of site will be included in the analytic models. Although we hope that equal proportions of co-users and non co-users present at each site, we understand that the fundamental differences between the Charleston metro area, Pickens County SC, and Florence exist and may cause some correlation between co-use group and study site. Assuming that the proportion of variance in co-use groups due to study site and other covariates may be moderate ($R^2=0.25$) and that attrition will not exceed 25%, we have adjusted our study sample size to account for this scenario. This increases our randomized sample to a total of 208 (139 cannabis co-users and 69 tobacco only users) accounting for both site correlations with co-use group and anticipated attrition. If site correlations with study outcomes or attrition are lower than pre-specified, our statistical power will exceed 80%. Specific Aim #2: Among co-users, assess changes in cannabis use during tobacco cessation treatment. Hypothesis 2: Co-users with moderate to high severity of nicotine dependence will demonstrate increases in concurrent cannabis use, while lower severity of nicotine dependence will yield no changes in cannabis use. To attain adequate power to assess Aim #2, a within co-use cohort comparison, the study will oversample the cannabis co-use cohort as compared to the tobacco only cohort (2:1). At screening, nicotine dependence will be assessed via the Fagerström Test for Nicotine Dependence (FTND) (92) and categorized accordingly: low nicotine dependence (0-4), medium or high nicotine dependence (5-6; 7-10). Cannabis use during the final 4 weeks of study treatment as compared to baseline use will be assessed among co-users. Based on our preliminary data from an ongoing adult tobacco cessation trial (R34 DA042228), we have nearly equivalent numbers of participants falling into low and moderate/high nicotine dependence categorizations (Mean=4.5; Median=5). Therefore, we anticipate ~40% will have medium/high nicotine dependence. With 208 participants, 139 in the cannabis co-use cohort (104 completers), we will achieve 80% power with a type 1 error rate of 5% to detect a between group cannabis use difference of Cohen's $d\approx0.6$ (Med/High nicotine dependence vs. low nicotine dependence).

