Primary Study Aims: Aim 1: To assess the difference in the log-odds of abstinence from tobacco at the end of treatment (Week 12) between baseline cannabis co-users compared to tobacco only participants, augmented inverse probability weighted logistic regression models will be developed. The inverse of the conditional probability of being in the cannabis co-use cohort will be included in the model to account for inherent imbalances between study groups and to reduce bias by resembling a randomized controlled trial. In addition to the inverse propensity weights, AIPW methods incorporate a covariate and study site adjusted model for the study group outcome (114). Aim 2: To assess the association of baseline nicotine dependence severity (Med/High nicotine dependence vs. low nicotine dependence) with cannabis use rates during study treatment, generalized linear mixed effects models will be assessed with cannabis use rates and amounts during the final 4 weeks of treatment as the primary indicator of cannabis use severity and nicotine dependence group as the primary model predictor. In addition to grouping by nicotine dependence severity, continuous levels of dependence severity (FTND score) will be modeled to assess possible linear and quadratic relationships between dependence severity and cannabis use. Following examination of the differences in end of treatment cannabis use rates based on baseline nicotine dependence, rates of cannabis use will be assessed by group (nicotine dependence severity) over all weekly study visits to determine if those with increased dependence severity exhibit a different trajectory (slope and pattern) of cannabis use during the entire study treatment. Model-based means and associated standard errors will be used to test group level differences. Exploratory Aim: To assess the relationship between baseline cannabis use severity and tobacco outcomes, generalized linear mixed effects models will be developed with weekly 7-day point prevalence abstinence from tobacco as the primary model outcome. In addition to tobacco abstinence, weekly average cigarettes per day will be examined as an indicator of use reduction differences over time. Longitudinal patterns in tobacco abstinence and use amounts will be modeled through the inclusion of baseline cannabis use severity indicators, study visit, and baseline tobacco use rates as model covariates. Additionally, differential effects over time will be examined with the inclusion of the interaction of cannabis use severity and study visit. Model-based means and associated standard errors will be used to test group level differences across the study treatment.

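### The exploratory severity models among co-users do not name baseline nicotine dependence or age as covariates, so residual confounding by dependence could produce part of a dose gradient

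*Combined protocol and SAP*

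**What the plan says.** The aim is stated in section 1.0: "To assess for a dose-dependent impact of cannabis use severity on tobacco cessation outcomes among co-users". The endpoint table in section 3.0 gives the same purpose, "to assess for dose-dependent impact on tobacco outcomes based on cannabis use severity", and defines severity by days of cannabis use in the 30 days before baseline.

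Under Primary Study Aims in section 10.0, "generalized linear mixed effects models will be developed with weekly 7-day point prevalence abstinence from tobacco as the primary model outcome", and weekly cigarettes per day is a further outcome. The named terms are "baseline cannabis use severity indicators, study visit, and baseline tobacco use rates as model covariates", followed by the interaction of severity with visit.

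Four other statements bear on this:

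- Section 10.0, Propensity Score Methods, expects co-users and tobacco-only users to differ in age, race, tobacco use severity and nicotine dependence. It uses a propensity score for being in the co-use group.
- Section 10.0, Power and sample size, says that "an additional fixed factor of site will be included in the analytic models". The Aim 1 text repeats this: "AIPW methods incorporate a covariate and study site adjusted model for the study group outcome". The exploratory text does not.
- Section 10.0, Statistical analyses, plans to look for baseline correlates of abstinence but gives no rule for taking them into any particular model.
- Section 2.0, A2, states: "Cannabis use has been associated with an increased risk of nicotine dependence and greater nicotine dependence among co-users".

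**The concern.** Severity of cannabis use is an observed, graded exposure. Confounding in this comparison is controlled only by what enters the model. The weighting used for Aim 1 does not help, because a score for co-use against no co-use says nothing about who uses heavily within the co-use cohort.

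The plan treats nicotine dependence as distinct from amount smoked: it lists the two separately as expected imbalances. Adjusting for baseline smoking rate therefore covers dependence only in part. If heavier cannabis users are also more dependent smokers, and more dependent smokers quit less often, a downward gradient in abstinence would appear with no effect of cannabis severity.

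What is at stake is how a gradient would be read. The pilot figures in section 2.0 (risk ratios of 1.7 for intermittent use and 4.2 for severe use, no adjustment stated) are already read there as abstinence falling with severity. The summary in section 2.0 says that the study's results will help guide tobacco treatment in co-users.

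**Working it through.** The documents give no sample size, power or effect size for the exploratory aim, so there is no figure to reproduce. The check asks how large a spurious gradient could be.

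**Inputs from the documents.** 139 co-users and 104 completers (section 10.0; 139 × 0.75 = 104.25). Abstinence of 20% in co-users, the Aim 1 planning rate, which gives 0.20 × 104 = 20.8 abstinent co-users at a visit.

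**Assumed inputs.** The correlation ρ of severity with FTND, the correlation r of baseline smoking rate with FTND, and the odds ratio for abstinence per SD higher FTND. This odds ratio is below 1, meaning more dependent smokers quit less often. The true severity effect is nil.

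**Approximation.** Put dependence D, smoking rate C and severity S on an SD scale, with S and C related only through D. The coefficient of S when D is regressed on S and C is

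b = ρ(1 − r²) / (1 − ρ²r²),

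and the spurious odds ratio per SD of severity, adjusting for C only, is about exp(b × ln OR_D).

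| ρ | r | OR_D | b | Spurious OR |
|---|---|---|---|---|
| 0.3 | 0.4 | 0.5 | 0.252/0.9856 = 0.256 | 0.84 |
| 0.4 | 0.4 | 0.5 | 0.336/0.9744 = 0.345 | 0.79 |
| 0.3 | 0.6 | 0.5 | 0.192/0.9676 = 0.198 | 0.87 |
| 0.4 | 0.6 | 0.5 | 0.256/0.9424 = 0.272 | 0.83 |
| 0.2 | 0.4 | 1/1.5 = 0.67 | 0.168/0.9936 = 0.169 | 0.93 |
| 0.2 | 0.6 | 0.67 | 0.128/0.9856 = 0.130 | 0.95 |

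**Simulation.** Single-visit logistic regression, n = 104, about 20% abstinent, outcome depending on D only, two-sided 5% test of severity.

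- ρ 0.3-0.4, r 0.4-0.6, OR_D 0.5, adjusting for smoking rate only: spurious odds ratio about 0.76-0.87, false positives about 6-15%.
- Weak confounding (ρ 0.2, OR_D about 0.67): about 0.93 and 6%.
- With FTND added: about 1.0 and 4-5%.

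A separate grid (ρ 0.2 or 0.4, r 0.5 or 0.7, OR_D 0.5 or 0.7; odds ratios from one large sample of 200,000, rejection rates from 600 runs of 104 per cell) agrees. Without FTND it gave odds ratios of 0.81-0.97 and false positives of 4-12%. With FTND it gave 0.99-1.02 and 4-5%. With ρ = 0 the odds ratio was 0.99-1.00, as it should be. At 600 runs the Monte Carlo standard error around 5% is √(0.05 × 0.95/600) = 0.9 percentage points, so rates of 4-6% cannot be told from nominal.

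The planned model is a longitudinal mixed model. The single-visit model is a simplification. Age and site were not simulated.

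**The case against.** The case for leaving the plan as it is has several parts.

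- **Site.** A reader might infer that site has been left out. The documents do not support that. The power text puts a site factor in the analytic models, and its wording is not confined to Aim 1. The exploratory text is silent, so this is something to confirm.
- **The list may not be complete.** The plan does not call it exhaustive, and a screen for correlates of abstinence is planned. This stands, but no rule carries the screen into this model, and choosing covariates after seeing the outcome is weaker than naming them.
- **Design limits.** Enrolment is restricted to ages 18-40 and to quit interest of at least 5 on a 10-point scale. This narrows confounding by age and motivation. It does not touch FTND.
- **The premise is not shown.** A reader might infer that heavier cannabis users in this cohort are known to be more dependent. Section 2.0 links cannabis use to dependence in general and gives no correlation with severity among co-users. In the adult pilot, co-users resembled tobacco-only users on several tobacco measures, though that compares groups, not severity levels.
- **FTND may be a mediator.** If cannabis use raises dependence, adjusting for FTND removes part of the effect of interest. This stands. It is the reason to report both estimates rather than replace one with the other.
- **Low stakes.** The aim is exploratory, with no hypothesis or power claim. This stands too and limits the weight of the point.

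**Conclusion.** The point holds as a gap in specification for an exploratory analysis. FTND and age are not named, the propensity score does not reach this comparison, and adjustment for baseline smoking rate leaves room for residual confounding by dependence. Under moderate assumed confounding the bias is modest but enough to look like a dose gradient; under weak confounding it is close to nothing. The case for age rests on the plan's own expectation of imbalance between the cohorts, not on a calculation.

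Two stronger readings should be resisted. One is that the pilot gradient is an artefact of dependence: the documents give no data to test that. The other is that the study's main result is at risk: Aim 1 has its own adjustment, which includes nicotine dependence, and is unaffected.

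**What to change.** In the exploratory paragraph of section 10.0, for both abstinence and cigarettes per day:

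1. Add baseline FTND as a covariate (first priority), then age.
2. State that the site factor promised in the power text applies to these models.
3. Report the severity estimate with and without FTND, and say beforehand that the two differ in meaning if FTND lies partly on the path from cannabis use to abstinence.

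The cost is a few lines of SAP wording; FTND and demographics are already collected at screening. The statistical cost is one parameter each for FTND and age, and two for site if the three locations in section 6.0 are kept separate: 1 + 1 + 2 = 4, against about 20 abstinent co-users per visit. The list should therefore stay short. Motivation to quit can be left out, since eligibility already restricts it.

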However, other studies have found no evidence of an adverse impact of cannabis on tobacco cessation (54-59), no differences in tobacco outcomes based on cannabis use frequency (42, 55), no impact on intentions to quit using tobacco (53, 60), and no adverse influence on the beneficial effects of low nicotine content cigarettes (61). This mixed literature on tobacco cessation outcomes supports the need to study co-use with a rigorous, prospective study design to better answer these important public health questions and inform the research and clinical care of tobacco use disorder. Currently, no prospective studies have evaluated the impact of cannabis use and its severity on tobacco cessation, which is a major objective of this proposed study.

A.2.b. Compensatory substance use among co-users. A treatment concern for co-users is the issue of compensatory (i.e., increased) use of the other, non-treated substance, during cessation. Among co-users, there are data exploring compensatory tobacco use during cannabis reduction/cessation (opposite relationship of the proposed study), though findings have been mixed. Some studies have shown compensatory use (increases in tobacco use during cannabis abstinence/reduction) (62-65), while our research group and others have found no evidence of compensatory tobacco use during cannabis cessation (66-68). We have also found individual differences associated with changes in tobacco use among; 1) those who concurrently reduced their cannabis use (69), and 2) those with lower levels of nicotine dependence (70). A recent study among co-users with schizophrenia found that compensatory use of tobacco was most pronounced in the first seven days of cannabis abstinence, but returned to baseline levels by Day 28 of abstinence (71). This study suggests that the relationship between these two substances may be complicated and transient and therefore must be studied with a design that captures changes in use of the non-treated substance. Patterns of compensatory use are important to determine as tobacco cessation could lead to greater cannabis use and associated adverse effects (72-76). There is a dearth of data available to address the issue of transient or sustained compensatory cannabis use and how reliably compensatory use occurs during tobacco treatment.

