B1. Study Overview. This proposed prospective tobacco cessation study will evaluate the impact of concurrent cannabis use and severity on tobacco abstinence among co-users and assess changes in cannabis use during treatment. Adult tobacco users (ages 18-40) who are motivated to quit smoking will be recruited. Cannabis co-users will be oversampled (2:1) and will be compared to tobacco only participants (using appropriate propensity score models). All participants will receive first-line tobacco cessation pharmacotherapy (varenicline) paired with a behavioral intervention to bolster abstinence rates (contingency management and psychosocial counseling) for a standard 12-week treatment period. Cannabis use will not be targeted with treatment. This is not a treatment outcome study per se and thus we are not evaluating (with a control group) an intervention. Rather, cannabis use status (co-use vs. not) is our independent variable. Biochemical verification of tobacco and cannabis use will be collected at screening and throughout the 12-week treatment period in addition to daily self-reports of use. Specifically, this study will: 1) examine the impact of cannabis co-use on tobacco cessation among co-users compared to tobacco only users (Aim #1); 2) with the use of frequent measurement, assess changes in cannabis use (among co-users) during tobacco treatment and determine if profiles of changes in cannabis use emerge (i.e., compensatory use, reduction, no change) (Aim #2); and 3) assess for a dose-dependent impact of cannabis use severity on tobacco cessation outcomes among co-users (Exploratory Aim).

It should be noted that while this is not a randomized and blinded study (cannabis co-use status will be known to research staff), it is important to not bias the results of the study. The hypothesis is that cannabis co-use will adversely impact tobacco cessation, but it's important to the scientific integrity of this study to obscure that hypothesis from study participants and manage biases with research staff. Staff will be educated about introducing bias into the study and methods to manage bias in non-randomized and non-blinded trials. For research participants, the aim of the study will intentionally broad and ambiguous to not

overtly influence their behavior and tobacco quit attempt. The title of the study and consent document, therefore, are not as specific as they would normally be to maintain the integrity of this research.

B2. Preliminary Studies.

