
Secondary Data Analysis: In addition to end of treatment point prevalence tobacco abstinence rates, similar analytic models will be used to assess abstinence rates at the 6-month follow-up visit. Additionally, longitudinal analysis of weekly tobacco abstinence will be assessed using repeated measures logistic regression models using a general estimating equations framework (GEE) (115) and working correlation

structures will be independently compared using the quasi-likelihood under the independence model criterion statistic (116). Similarly, the number of smoking days per week and cigarettes per day will be collected via daily diaries and compared between co-use cohorts using generalized linear mixed effects regression models. Finally, weekly cannabis and tobacco use will be collected to develop group-based trajectory models and time naïve covariates will be used to determine group membership. Additionally, changes in cannabis craving, withdrawal, use, and subjective effects during treatment with varenicline will be examined in the cannabis co-use group. Specifically, changes in cannabis craving, withdrawal (synchronous effects of varenicline) and cannabis use severity (substitution) will be assessed for correlations with changes in tobacco use. Generalized linear mixed effects models will be developed with cannabis use outcomes and the time varying effects of tobacco use as the primary independent variable. Further, noting possible differences in the relationship between tobacco outcomes and combustible/non-combustible cannabis use, model effect modification will be assessed using cannabis use type groupings (primarily combustible vs. primarily non-combustible). All analyses will be conducted using SAS version 9.4 (SAS Institute, Cary, NC, USA).

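### The one stated regression of cannabis use on time-varying tobacco use does not separate within-person from between-person effects, and leaves the time unit and study week unstated

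*Combined protocol and SAP*

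**What the plan says.** Section 10.0, Secondary Data Analysis, states the model in one sentence, as a generalized linear mixed model with "cannabis use outcomes and the time varying effects of tobacco use as the primary independent variable". It names no person-mean or deviation term, time unit, lag, random slope or study-week term. By contrast, the Exploratory Aim model in the same section lists study visit among its covariates.

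Two neighbouring analyses also use both substances. Changes in cannabis craving, withdrawal and use severity (the last labelled as substitution) "will be assessed for correlations with changes in tobacco use". Separately, "weekly cannabis and tobacco use will be collected to develop group-based trajectory models"; whether these are joint or separate models is not stated.

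The declared Aim 2 model regresses cannabis use in the final four weeks on baseline nicotine dependence group, and then compares cannabis trajectories over all weekly visits by that group. It contains no on-treatment tobacco term.

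On direction, Section 2.0 (A2) reports that "Cannabis use has been associated with an increased risk of nicotine dependence and greater nicotine dependence among co-users". Section 2.0 (A.2.b) says "A treatment concern for co-users is the issue of compensatory (i.e., increased) use of the other, non-treated substance, during cessation" and warns that "tobacco cessation could lead to greater cannabis use and associated adverse effects". The Study Overview (B1) leaves the direction open: the study will "determine if profiles of changes in cannabis use emerge (i.e., compensatory use, reduction, no change".

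**The concern.** Compensation is a statement about one person over time: when this co-user smokes less, does this co-user use more cannabis? That is a negative within-person slope. Whether co-users who smoke more on average also use more cannabis is a different question, and the Background makes a positive answer plausible. A random-intercept model with one uncentred tobacco term does not keep the two apart. It returns a single slope that mixes them, with weights set by the variance structure and the number of time points.

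If the signs differ, the mixed slope understates compensation. The declared Aim 2 model has no tobacco term, so this is the only stated regression that would quantify how cannabis use moves with a co-user's own smoking. As written, both a split and an unsplit version satisfy the plan, and they can give different answers.

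Study week raises a related problem. All participants share a Day 8 target quit date (Section 9.0), so tobacco use should fall at about the same time for everyone. Without a week term, any common trend in cannabis use loads onto the tobacco slope. With one, part of the common tobacco drop is absorbed.

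**Working it through.** The plan gives no effect size, power or variance figure for this model, so there is no stated figure to reproduce.

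**Inputs from the documents (Sections 9.0 and 10.0).** 104 co-user completers; diaries completed daily through Week 12, hence T = 12 weekly or T = 84 daily points.

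**Assumed inputs.** Within-person slope bw = -0.3 and between-person slope bb = +0.3. Tobacco intraclass correlation (ICCx) 0.3 to 0.9. Cannabis intraclass correlation given tobacco (ICCy) 0.3 to 0.7.

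**Formula.** In a random-intercept model with one uncentred covariate, between-person information is down-weighted by

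θ = (1 - ICCy) / [(1 - ICCy) + T·ICCy].

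The weight on the between-person slope is

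w = θ·T·ICCx / [(T - 1)(1 - ICCx) + θ(T·ICCx + 1 - ICCx)].

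The reported slope is bw + w(bb - bw). The proportional loss is w(1 + bb/|bw|). The slope reaches zero when bb/|bw| = (1 - w)/w.

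**Mid-range cell, weekly (ICCs 0.5/0.5, T = 12).** θ = 0.5/6.5 = 0.077. w = 0.4615/(5.5 + 0.5) = 0.077. Slope = -0.3 + 0.077 × 0.6 = -0.254, a loss of about 15%. The between slope would have to be 12 times the within slope to cancel it.

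**Same cell, daily (T = 84).** w = 0.012; slope -0.293; loss about 2%.

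**Most extreme cell (ICCx 0.9, ICCy 0.3).** Weekly: θ = 0.7/4.3 = 0.163; w = 1.758/(1.1 + 1.774) = 0.612; slope +0.067. Daily: w = 0.197; slope -0.182.

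**Full weekly grid, slope (weight on the between slope):**

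| ICCx | ICCy 0.3 | ICCy 0.5 | ICCy 0.7 |
|---|---|---|---|
| 0.3 | -0.258 (7.0%) | -0.279 (3.4%) | -0.291 (1.6%) |
| 0.5 | -0.211 (14.9%) | -0.254 (7.7%) | -0.278 (3.6%) |
| 0.7 | -0.126 (29.0%) | -0.202 (16.3%) | -0.252 (8.0%) |
| 0.9 | +0.067 (61.2%) | -0.043 (42.9%) | -0.149 (25.2%) |

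The sign reverses in 1 of 12 cells. With daily data the slope runs from -0.30 to -0.18 and never reverses. With only four weekly points it runs from -0.27 to +0.18 and reverses in 4 of 12 cells.

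**Other slopes.** With bw = -0.2, bb = +0.4, ICCx 0.5 to 0.8 and ICCy 0.3 to 0.7 over 12 weeks, the between weight is 4% to 42% and the slope -0.18 to +0.05, reversing in 1 of 6 cells. That cell with daily data has a weight of about 10% and a slope of -0.2 + 0.10 × 0.6 = -0.14. A relatively larger between slope costs more: at 0.5/0.5 with bw = -0.1 and bb = +0.3, the loss is 0.077 × (1 + 3) = 31%.

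**Simulation check** (104 people, 12 weeks, Gaussian outcome, 40 runs per scenario):

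| bw, bb; ICCx/ICCy | Single term: mean | Single: sig. negative | Single: sig. positive | Split within term: sig. negative |
|---|---|---|---|---|
| -0.3, +0.3; 0.5/0.5 | -0.265 | 100% | 0% | 100% |
| -0.3, +0.3; 0.9/0.3 | +0.059 | 0% | 17% | 97% |
| -0.1, +0.3; 0.5/0.5 | -0.071 | 75% | 0% | 95% |
| -0.1, +0.3; 0.8/0.3 | +0.058 | 0% | 28% | 35% |

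For a true -0.3, the split model's mean within-person slope was -0.29 to -0.31. In the last row the split removes the misleading positive results, but power for so weak an effect stays low.

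**The case against.** **Other analyses cover compensation.** A reader might infer that this model is the plan's only link between the two substances, or the only place where compensation is tested. The documents do not support that. Hypothesis 2 compares final-four-week cannabis use with baseline by dependence group, and is the declared test. The sentence just before this model correlates changes with changes, which removes stable differences between people. This objection stands, and it confines the point to one secondary model. It does not settle how that model is to be fitted.

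**The single term is inferred.** A reader might also infer that the plan has committed to one blended term. It has not: it is silent, and the plural wording about time-varying effects could cover several terms. The accurate criticism is under-specification.

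**Opposite signs are not established.** The Background links cannabis use to nicotine dependence but gives no slope of on-treatment smoking on cannabis amount among co-users. The preliminary trial data in Section 2.0 (B2), where abstinence fell as cannabis severity rose, make a positive between-person association plausible without giving its size. The within-person direction is left open in B1. This stands, but separate terms are useful whichever sign holds.

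**Reversal is not the typical result.** A reader might conclude that real substitution would be reported with the wrong sign. That needs assumed slopes together with mostly between-person tobacco variation and few time points, and a weak within-person effect makes it easier. Milder attenuation is more typical, and daily data largely remove it.

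**Parts of a remedy are matters of preference.** Week terms absorb some of the common quit-date drop, and a one-week lag could miss same-week substitution. Both points are fair and are reflected in the fix.

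**Conclusion.** The point holds as a specification gap in one secondary model. Fitted as a single uncentred term with a random intercept, the tobacco slope blends two associations. If the between-person association is positive and the within-person one negative, the slope is biased toward zero. With equal and opposite assumed slopes, the loss is about 15% at mid-range correlations over 12 weeks and about 2% with daily data. It becomes large when most tobacco variation lies between people, with reversal confined to the extreme of the weekly grid. All slopes and correlations are assumptions, and the formula and simulation are for a Gaussian outcome, so the size will differ for counts or binary outcomes. Aim 1, the declared Aim 2 test and the change-on-change correlations are not affected by this blending. The change is worth making because it is cheap and uses data already collected.

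**What to change.** In Section 10.0, Secondary Data Analysis:

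- State the time unit (day or week) for the mixed models of cannabis use on tobacco use.
- Enter tobacco use as two terms: each co-user's own mean over the analysis period, and the deviation from that mean at each time point.
- Name the within-person coefficient as this model's estimate of compensation, and report the between-person coefficient beside it.
- Report the within-person coefficient with and without study week, and explain that the shared Day 8 quit date makes the two answer slightly different questions.

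A lagged version and an interaction with FTND score are optional sensitivity analyses.

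The cost is SAP wording and one extra derived variable. No new data are needed, and the sample size is unchanged.
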